13.3 Analyses of secondary endpoints

Disease-free survival (DFS) is defined as the time period from the date of R0 resection to the date of disease recurrence or death will be calculated as disease-free survival (DFS). DFS will be calculated using the Kaplan-Meier method, and then compared by the log-rank test. The rate of R0 resection, incidence of complications, and peritreatment mortality will be compared with the Chi-square test (or Fisher's exact test, if indicated).

13.4 *P* value

According to the O'Brien-Fleming algorithm, the two-sided significance level will be 0.000527 in the first interim analysis and 0.014 in the second interim analysis. The final significance level will be 0.045.

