4.0 ENDPOINTS

The primary endpoint is overall survival. The time from the date of randomization to the date of death or the last follow-up will be calculated as overall survival (OS).

As to secondary endpoints, we aim to compare disease-free survival (DFS), safety, rate of R0 resection, and pathologic response. The time from the date of R0 resection to the date of disease recurrence or death will be calculated as disease-free survival (DFS).

The toxicity of chemotherapy and radiotherapy will be evaluated according to the National Cancer Institute Common Terminology Criteria for Adverse Events Version 3.0 (CTCAE v 3.0). Perioperatively, the following will be evaluated: type of procedure, surgical resection rate, operation time, blood loss, thoracic drainage fluid volume, hospital stay, incidence of complications, and perioperative mortality.

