10.1.9 Timing of surgery

Approximately 4–6 weeks after completion of CRT, surgery will be performed if the patient's white blood cells, platelets, and liver and kidney function have all returned to normal. Routine blood tests, blood biochemical examinations, chest and abdominal CT scans, detection of lung function, and electrocardiograms will be performed before surgery.

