10.2 Protocol for patients receiving surgery alone

Surgery will be conducted soon after the randomization. McKeown or Ivor Lewis esophagectomy will be performed. Two-field lymphadenectomy with total mediastinal lymph node dissection is performed during sugery. Radical resection will be defined by both macroscopic observation and postoperative pathological negative margin. A jejunum tube will be placed via the nose or by jejunostomy.

The lymph nodes resected during total lymphadenectomy include the left recurrent laryngeal nerve nodes, right recurrent laryngeal nerve nodes, infraaortic arch nodes, periesophageal nodes of the upper, middle and lower thoracic portion, the infracarinal nodes, the posterior mediastinal nodes, the paracardiac nodes, lesser curvature nodes, the left gastric nodes, the common hepatic nodes, the splenic nodes and the celiac nodes.

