13.0 STATISTICAL ANALYSIS

All patients will be included in the analysis whether they complete the treatment protocol or not. Data analyses will be done according to the 'Intention to treat' principle.

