14.0 FOLLOW-UP

The full-time study nurses will be responsible for the registration, follow-up of patients and inputting data of CRF. Then they will submit the information to the central office for further analysis. Each patient should have their own archive for evaluation (CRF), and a full-time study nurse will be responsible for the follow- up of each patient, as well as registration, inputting and preservation of information.

After the treatment has ended, patients will be re-examined in the hospital clinics once every 3 months within 1 year. Thereafter they will have regular follow-up visits once every 6 months until their deaths or the study ends. Physical examination, tumor markers, chest x-ray, Esophageal barium x-ray, cervical/abdominal ultrasonography will be performed at follow-up visits. Neck/chest/abdominal CT with contrast and EGD will be performed once every year.

Note: Patients who withdraw from this treatment protocol will also be followed up, and included for statistical analysis. History of the study protocol changes are shown in the *Appendix*.

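### DFS is timed from R0 resection, so its log-rank test compares groups selected after randomisation (secondary endpoint only; OS is unaffected)

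*Protocol*

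**What the plan says.** Section 13.3 states that DFS "is defined as the time period from the date of R0 resection to the date of disease recurrence or death". Section 4.0 gives the same definition, so this is not a slip in one place. Section 13.3 continues: "DFS will be calculated using the Kaplan-Meier method, and then compared by the log-rank test". It also compares the R0 resection rate between arms as an outcome.

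Section 13.0 sets the general rule: "All patients will be included in the analysis whether they complete the treatment protocol or not". It adds: "Data analyses will be done according to the 'Intention to treat' principle". Section 14.0 notes: "Patients who withdraw from this treatment protocol will also be followed up, and included for statistical analysis".

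The route to surgery differs by arm. In ARM 1, 10.1.3 schedules 4 weeks of radiotherapy, and 10.1.9 places the operation about 4-6 "weeks after completion of CRT, surgery will be performed". For ARM 2, 10.2 says: "Surgery will be conducted soon after the randomization". Overall survival (OS), by contrast, runs from randomisation (4.0 and 13.2).

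**The concern.** A patient who is never operated on, or whose resection is not R0, has no DFS start date, and no rule covers that patient. The definition therefore limits the log-rank test to patients who reached R0.

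Reaching R0 happens after randomisation and can depend on treatment. Some conditions before surgery exist only in ARM 1: becoming unfit for surgery after chemoradiotherapy (6.3 d), the radiation toxicities that end protocol treatment (10.1.4, item 4), and recovery of blood counts and of liver and kidney function before the operation (10.1.9). Metastasis found during treatment (6.3 a) also has longer to appear before surgery in ARM 1. Chemoradiotherapy may in turn change how many tumours can be completely removed.

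Randomisation balances the 215 and 215 patients allocated, not the subsets who reach R0. A DFS p value from those subsets would be read as randomised evidence. It could show a difference where there is none, or hide a real one.

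**Working it through.** The protocol gives no DFS event count, power or R0 rate, so there is no DFS figure to reproduce.

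**1. Start of the clock.** In ARM 1, surgery comes 4 + 4 = 8 to 4 + 6 = 10 weeks after chemoradiotherapy starts. At 30.44 days per month, 8 × 7 / 30.44 = 1.8 and 10 × 7 / 30.44 = 2.3 months. The difference between arms is this less ARM 2's short wait, for which no figure is given. An interruption of two weeks (10.1.4, item 5) makes 12 weeks, or 12 × 7 / 30.44 = 2.8 months.

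**2. Patients without a DFS time.** This range is an assumption. If 70-90% reach R0, then 0.10 × 215 = 21.5 to 0.30 × 215 = 64.5, or about 22 to 65 patients per arm, have no DFS time. The number may differ between arms.

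**3. Does the later start matter by itself?** Let T be time from randomisation to failure and S the time of surgery. With a constant hazard λ shared by all patients,

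P(T > S + t | T > S) = exp(−λ(S + t)) / exp(−λS) = exp(−λt).

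This does not depend on S. The time taken off each ARM 1 patient is balanced by removing those who fail before surgery. A simulation with surgery at 2.5 and 0.5 months and no frailty agrees: HR 1.00 and about 5% false positives. If patients differ in frailty, the later operation removes more frail patients from ARM 1 and the HR falls to about 0.97-0.98. So the later start acts mainly through selection.

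**4. Size with no treatment effect.** All inputs are assumed: 215 per arm, median failure time 24 months from randomisation, log-normal frailty with SD 0.8, surgery at 2.5 (ARM 1) and 0.5 months (ARM 2), censoring uniform over 24-108 months. The correlation between frailty and not reaching R0 was varied from 0 to 0.8.

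| Lacking R0, ARM 1 vs ARM 2 | Spurious HR, correlation 0 to 0.8 | Two-sided false positives (nominal 5%) |
|---|---|---|
| 20% vs 10% | 0.97 to 0.90 | about 5% to 13% |
| 10% vs 25% | 0.97 to 1.09 | about 6% to 9% |
| 10% vs 10% | about 0.97 | about 6% |

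A repeat with these inputs agreed to within about 0.01 in the HR and about 2 percentage points in the error rate.

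**5. A second model.** Gamma frailty (shape 2), median 30 months, ARM 1 surgery 9 weeks later, and one fixed, fairly strong link between frailty and R0. By assumed R0 rate (ARM 1 vs ARM 2):

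- 90% vs 90%: HR 0.98, 5.8% false positives
- 80% vs 90%: HR 0.91, 12%
- 70% vs 90%: HR 0.84, 23%
- 90% vs 80%: HR 1.08, 8.5%

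In the same runs, a log-rank test of failure time from randomisation in all 430 patients gave HR about 1.00 and 4-6% rejection. That benchmark did not count missing R0 as an event, so it shows the effect of keeping everyone on one clock. It does not simulate the endpoint proposed below.

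**The case against.** DFS is a secondary endpoint with no hypothesis or power attached, and OS runs from randomisation. Patients who fail before surgery still count in OS, in the R0 rate and in peritreatment mortality. This stands, and it limits the severity: the primary conclusion is not at risk.

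A reader might infer four stronger things that the protocol does not support.

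- **That the R0 rate is expected to differ.** The protocol plans to compare it but states no expected rate or direction.
- **That the two-month later start is a defect in its own right.** Step 3 shows that the shift alone gives HR 1.00. The 0.97-0.98 seen with equal exclusion comes from removing frail early failures.
- **That the protocol orders non-R0 patients to be dropped, in flat contradiction of 13.0.** It never says so; the exclusion follows from their having no start date. Nor can the general rule apply literally to every secondary outcome: tumour regression grade (10.3) is defined only for patients given preoperative chemoradiotherapy. The exact statement is that the DFS definition cannot be reconciled with 13.0 and 14.0 for a between-arm test.
- **That false positives are known to be about 10%.** With a weak link between frailty and R0 (correlation 0.3), they are 5-8% across the unequal scenarios.

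A change also has limits. Restaging before surgery is specified only for ARM 1 (10.1.8), and follow-up visits count from the end of treatment (14.0). Timing from randomisation therefore does not fully align assessments between arms. This stands and belongs with the fix.

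**Conclusion.** The point holds as one that should be fixed, for a secondary endpoint only. The planned DFS log-rank test depends on reaching R0 resection, an outcome that treatment can change and that the protocol itself compares between arms. It is therefore not a randomised comparison. This follows from a definition stated twice, not from detail left to an analysis plan.

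Selection drives the problem. Its direction is not fixed: the spurious HR falls below 1 when ARM 1 loses more poor-prognosis patients and can rise above 1 when ARM 2 does. The size rests on assumed R0 rates, frailty and correlation. It ranges from negligible (HR about 0.97, false positives 5-6%) to material (HR 0.90 and about 13% at 20% vs 10% lacking R0; more under a wider imbalance). None of these figures is an estimate for this trial.

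**What to change.** In 4.0 and 13.3, define the endpoint to be compared from the date of randomisation, in all randomised patients, with these events:

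- no R0 resection for any reason, including progression before surgery, counted at one common fixed time after randomisation in both arms;
- recurrence;
- death.

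The fixed time should fall after surgery is due in ARM 1, allowing for interruptions (12 weeks from the start of chemoradiotherapy in step 1, plus any wait before it starts). Keep DFS from R0 resection as a description of resected patients, without a between-arm p value.

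Add a sensitivity analysis that assigns recurrences to common time windows from randomisation. The common time for preoperative failure limits the effect of the unequal restaging and visit schedules; this analysis checks what remains.

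**Cost.** No new patients and no change to treatment. Absolute figures will be lower than DFS from R0, and a true difference in R0 rate will count as part of the effect. The amendment needs ethics re-approval (11.2). Recruitment was planned to end in December 2014 and the last listed amendment is dated December 2015, so a change made after that would follow accrual. It should be dated, and the report should say whether it preceded any comparison of DFS by arm. Section 14.0 provides for following patients who withdraw, but the protocol does not show that every date needed is recorded; check this against the case report form.

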13.5 Interim analysis

- 13.5.1 An independent Data Monitoring Committee will be appointed to monitor the study and make decisions regarding possible early closure and publication.
- 13.5.2 The Committee will meet at least once a year (or discuss via electronic means) to ensure no undue toxicity and to monitor the data quality and results. Only this committee will be allowed access to the data until the decision is made to release the results.
- 13.5.3 Two formal interim analyses will be performed on 1 June, 2011 and 31 December, 2015.
- 13.5.4 The interim analysis of survival and toxicities will be reviewed by the committee. These results will not be the sole criteria for deciding whether to terminate accrual or report results early. All decision will also take into account the characteristics of patients, the nature of any toxicity, relevant external results, and other pertinent information.
- 13.5.5 Reports of the results will be made corresponding to the required number of events in the sample size calculation section of the protocol (about universal 2-year follow-up), and again after universal 5-year follow-up.
- 13.5.6 An Executive Committee composing of all the study coordinators will meet (or discuss via electronic means) every 6 months to monitor the patient accrual rate and to solve practical problems encountered during conduction of the trial.
- 13.5.7 Earlier and more frequent meetings will be called if excessive toxicities are observed.

14.0 FOLLOW-UP

The full-time study nurses will be responsible for the registration, follow-up of patients and inputting data of CRF. Then they will submit the information to the central office for further analysis. Each patient should have their own archive for evaluation (CRF), and a full-time study nurse will be responsible for the follow- up of each patient, as well as registration, inputting and preservation of information.

After the treatment has ended, patients will be re-examined in the hospital clinics once every 3 months within 1 year. Thereafter they will have regular follow-up visits once every 6 months until their deaths or the study ends. Physical examination, tumor markers, chest x-ray, Esophageal barium x-ray, cervical/abdominal ultrasonography will be performed at follow-up visits. Neck/chest/abdominal CT with contrast and EGD will be performed once every year.

Note: Patients who withdraw from this treatment protocol will also be followed up, and included for statistical analysis. History of the study protocol changes are shown in the *Appendix*.

Appendix

Modifications of the Study Protocol

Date	Before modification	After modification	Location
October 20, 2011	6.1 Inclusion criteria d. Patients aged from 18 to 60	6.1 Inclusion criteria d. Patients aged from 18 to 70	P8
October 20, 2011	13.5 Interim analysis 13.5.1 The Office of Good Clinical Practice from Sun Yat-sen University Cancer Center will monitor the study and make decisions regarding possible early closure and publication Interim analysis.	13.5 Interim analysis 13.5.1 An independent Data Monitoring Committee will be appointed to monitor the study and make decisions regarding possible early closure and publication.	P19
June 26, 2013	13.1 Sample size: 640 patients should be enrolled	13.1 Sample size: 430 patients should be enrolled	P18
December 1, 2015	13.3 Analyses of secondary endpoints The rate of R0 resection will be compared by the t test.	13.3 Analyses of secondary endpoints The rate of R0 resection will be compared by the Chi-square test.	P18
